#### **10.2.5 Physical Examination**

A physician or suitably trained qualified assistant will perform a complete physical examination, including voluntary photography of skin lesions due to scratching, at Visits 1, 3, 6, and 9. A skin examination will be conducted at Visits 1, 3, 4, 6, 9, and 10 (see [Table 1](#)).

A complete physical examination will include assessment of general appearance, eyes, ears, nose, throat, head/neck/thyroid, lymph nodes, cardiovascular, lungs/chest, abdomen, genitourinary, extremities, skin, musculoskeletal, neurologic, and other.

Skin will be examined thoroughly and excoriations/scratch marks recorded.

#### **10.2.6 Vital Signs**

Evaluation of vital signs will be performed at all visits. This includes blood pressure (systolic and diastolic), pulse, respiratory rate, temperature, height (or length depending on age), and body weight (using a certified weight scale) at clinic visits. BMI will be calculated.

#### **10.2.7 Abdominal Ultrasound**

Ultrasound of the liver and spleen will be performed at randomization (Visit 3) and at EOT (Visit 9). Liver size, echogenicity, and presence of masses/nodules as well as spleen size will be recorded.

#### **10.2.8 Overdose**

A4250 is minimally absorbed and has a very low systemic availability. Based on toxicology data, for study purposes any dose exceeding a total of >3 mg/kg body weight of A4250 taken as a single dose or as a cumulative dose within 24 hours is defined as an overdose.

The no-adverse-effect dose level in the most sensitive species (defined as 20 mg/kg/day) in the rat 1 month toxicity study gives a human equivalent dose of approximately 194 mg/day in

a 60 kg person. This dose is approximately 10-fold higher than the maximum possible dose predicted in human studies (20 mg).

The investigator/investigative staff should immediately and not later than within 24 hours of knowledge of the overdose, be reported by the investigator or delegate on the SAE report form. In the event of an A4250 overdose, the patient should be monitored closely.

### **10.2.9 Pregnancy**

If a pregnancy is discovered in a female patient enrolled in the study before the end of dosing, the patient will be immediately discontinued from the study and will attend the same visits as a prematurely withdrawn patient. If the pregnancy is discovered in a female patient enrolled in the study after the end of dosing, the patient will continue in the study per protocol. If a pregnancy occurs in a male patient's partner at any time during the study, the pregnancy should also be reported and followed.

Pregnancy is not considered to be an AE. However, if the patient has been dosed with the study drug, the pregnancy must be reported on the Paper Pregnancy Notification Form immediately within 24 hours after recognition to Safety Manager (please refer to [Section 10.1.3](#)). Date of exposure and as far as possible, details of the period of gestation at the time of exposure must be given.

The pregnancy should be followed to determine outcome, including spontaneous termination, details of birth, and presence of any birth defects, congenital anomalies or newborn or maternal complication. The infant who was exposed in-utero will be followed for up to 2 years after delivery. Individual cases with an abnormal outcome in association with the study drug should be reported on an expedited basis, i.e., reported rapidly to a competent authority.

## 11 STATISTICAL EVALUATION

All personnel involved with the analysis of the study will remain blinded until database lock for the double-blind Treatment Period and until major protocol violations have been identified.

All statistical analyses will be performed using SAS version 9.3 or higher.

### 11.1 Sample Size and Power

For the EU and RoW, the primary analysis will relate to the serum bile acid responder endpoint. For the US, the primary analysis will relate to the pruritus endpoint. For each primary endpoint, a pooled analysis for the closed testing procedure will be applied to control the 1-sided overall type I error rate for two treatment comparisons vs. the placebo at the 0.025 level (Kane et al, 2015, Lehmacher et al, 1991, and Marcus et al, 1976). The study will enroll 60 to 70 patients in order to obtain at least 20 evaluable patients in each arm. For each primary endpoint, simulations with 5000 iterations using 20 patients per arm were conducted to estimate the power after multiplicity adjustment, resulting in a standard error of <0.7% for each estimated power.

Based on the Phase 2 A4250-003 study data both dose groups are predicted to have similar treatment effects for both serum bile acids and pruritus. For serum bile acids, simulated proportions were analyzed using the CMH test to generate the following 1-sided p-values: both A4250 arms pooled vs. placebo, low dose vs. placebo, and high dose vs. placebo. Assuming 60% responders in the A4250 arms and 10% responders in the placebo arm, the power to claim significance for a particular A4250 arm after multiplicity adjustment is approximately 94%. The power to claim significance for at least one arm or both arms are approximately 99% and 91%, respectively.

For the proportion of positive pruritus assessments at the subject level in pruritus scores, simulated proportions were analyzed using ANCOVA to generate the following 1-sided p-values: both A4250 arms pooled vs. placebo, low dose vs. placebo, and high dose vs. placebo. With an effect size of 1.0526, the simulated power to claim significance for a particular arm after multiplicity adjustment is approximately 89%. The probability to claim significance for at least one arm or both arms are approximately 95% and 83%, respectively.

### 11.2 Statistical Methods

#### 11.2.1 Statistical Analysis Sets

##### Safety Analysis Set

The safety analysis set will consist of all patients who received at least 1 dose of study drug. Patients will be analyzed according to the treatment they actually received. The safety analysis set will be the primary analysis set for safety analyses.

##### Full Analysis Set

The full analysis set (FAS) will consist of all randomized patients who received at least 1 dose of assigned treatment. Patients will be analyzed in the treatment group they were randomized to even if they received incorrect study drug. The FAS will be the primary analysis set for efficacy analyses.

### **Per Protocol Analysis Set**

The per protocol (PP) analysis set is a subset of the FAS, and will consist of all randomized patients for whom no major protocol violation (no violation which may affect the study efficacy outcome) is documented. The PP analysis set will provide supportive data for the efficacy analyses.

Allocation of patients to the PP analysis set will be performed before unblinding of the study.

## **11.2.2 Methods of Statistical Analyses**

### **11.2.2.1 General Principles**

The primary objective of this study is to demonstrate the efficacy of repeated daily doses of 40 µg/kg/day and 120 µg/kg/day A4250 in children with PFIC Types 1 and 2.

In the EU and RoW, for the primary efficacy variable of fasting bile acid responder endpoint (at least a 70% reduction in fasting s-BA concentration or reaching a level  $\leq 70$  µmol/L at the end of treatment), the Cochran Mantel Haenszel (CMH) test stratified by PFIC class and age class will be performed to compare the proportion in fasting bile acid responder endpoint at the end of treatment (Week 22 and 24) in the two A4250 dose groups to placebo group. To ascertain that all data are used in the CMH analysis, neighboring strata will be pooled if all subjects in a stratum have the same response. Dropouts will be treated as non-responders. The proportion together with corresponding 95% CI, odds ratio and corresponding 95% Clopper-Pearson exact CI and p-value for the CMH test will be presented.

In the US, for the primary efficacy variable of the proportion of positive pruritus assessments at subject level over the 24-week treatment period, an analysis of covariance (ANCOVA) will be used. The model will include treatment arm, AM baseline pruritus score, PM baseline pruritus score, and randomization stratification factors, i.e. PFIC class and age class. LS mean(SE) by treatment arm and LS mean difference (SE), 95% confidence intervals, and p-values (where applicable) between treatments (120 µg/kg/day and 40 µg/kg/day, respectively) vs. placebo will be provided. If there are concerns on model assumptions, i.e. normality and homogeneity of variances, a non-parametric ANCOVA based on the rank scores will be used as a sensitivity analysis. LS mean/SE on the outcome by treatment arm and LS mean difference/SE between active dose and placebo will be provided.

The procedure for multiplicity adjustment is specified as follows:

In the closed testing procedure, the low and high dose groups will be pooled to compare with the placebo group first. If the 1-sided p-value is  $\leq 0.025$ , the 1-sided p-values for low dose vs.

placebo and high dose vs. placebo will be calculated, respectively. If both individual p-values are  $\leq 0.025$ , a significant treatment effect will be declared on both dose groups. If only one of them is  $\leq 0.025$ , a significant treatment effect will be declared on the corresponding dose group.

Other secondary and exploratory outcome variables will provide supportive efficacy and safety information regarding the differences between the treatment groups. No adjustments will be performed for multiple comparisons when testing secondary and exploratory efficacy variables.

If not otherwise specified, the baseline value of a parameter is defined as the last assessment of that parameter prior to the first intake of study treatment.

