## **6 STUDY OBJECTIVES**

### **6.1 Primary Objectives**

To demonstrate the efficacy of repeated daily doses of 40 µg/kg/day and 120 µg/kg/day A4250 in children with PFIC Types 1 and 2, as determined by the following:

- The proportion of patients experiencing at least a 70% reduction in fasting s-BA concentration from baseline to end of treatment or reaching a level  $\leq 70$  µmol/L compared to placebo after 24 weeks of treatment
- The proportion of positive pruritus assessments at the subject level over the 24-week treatment period.

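### Both primary objectives are powered, but in each region one is tested only as an unadjusted secondary; a serial gate would make it confirmatory at no cost to the regional primary

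*Protocol*

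**What the plan says.** Protocol section 6.1 lists two primary objectives, with no regional qualification: "The proportion of patients experiencing at least a 70% reduction in fasting s-BA concentration from baseline to end of treatment" (or reaching 70 µmol/L or less), and "The proportion of positive pruritus assessments at the subject level over the 24-week treatment period". The synopsis lists the same two.

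Sections 9.1.1, 9.1.2 and 11.1 then divide them by region. "For the EU and RoW, the primary analysis will relate to the serum bile acid responder endpoint", with pruritus as the first-listed secondary. "For the US, the primary analysis will relate to the pruritus endpoint", with s-BA response as the first-listed secondary.

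The multiplicity procedure works inside one endpoint: "For each primary endpoint, a pooled analysis for the closed testing procedure will be applied". Its stated aim covers the dose comparisons only, namely that it should "control the 1-sided overall type I error rate for two treatment comparisons vs. the placebo at the 0.025 level". Its first step is that "the low and high dose groups will be pooled to compare with the placebo group first"; each dose is then tested at 0.025. No rule connects the two endpoints within a region.

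Section 11.2.2.1, and the synopsis in the same terms, closes the matter: "No adjustments will be performed for multiple comparisons when testing secondary and exploratory efficacy variables".

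**The concern.** The trial sets out to demonstrate efficacy on two endpoints. It has about 90% power per dose on each and has already written the dose-level test for each. Yet for any one region the plan provides a controlled test of only one of them, and a stated rule puts the other outside error control. This is not a matter left open for the SAP: an SAP that ordered the two endpoints would contradict section 11.2.2.1 and the synopsis.

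The stake is the status of the second endpoint. However strong the pruritus result, for EU/RoW it is a nominal finding; the same goes for s-BA response in the US. If readers nevertheless treat a significant second endpoint as established, that inference has no error rate behind it.

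**Working it through.** **Inputs from section 11.1:** 20 patients per arm; one-sided 0.025; s-BA responders 60% in each active arm and 10% on placebo; pruritus effect size 1.0526, read as difference over SD.

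**Assumed, because the documents do not give them:** endpoint correlation within patient 0 to 0.5; responder rate under the null 10% to 50%. The simulations use an unstratified CMH test without continuity correction for s-BA and t tests without covariates for pruritus.

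**1. The plan's own power figures reproduce.**

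| Endpoint | | Particular dose | At least one | Both |
|---|---|---|---|---|
| s-BA | stated | 94% | 99% | 91% |
| s-BA | simulated | 94.9% | 98.3% | 91.5% |
| Pruritus | stated | 89% | 95% | 83% |
| Pruritus | simulated, two-sample t | 89.5% | 95.8% | 83.2% |

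With a variance pooled over the three arms, the pruritus figures are about 90%, 96% and 84%.

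**2. Error across the two endpoints as the plan stands, if the second were treated as a claim.** The bound is 0.025 + 0.025 = 0.05; for independent endpoints it is 1 - (1 - 0.025)² = 0.0494. Simulated with no effect on either endpoint:

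| Null responder rate | s-BA alone | Pruritus alone | Either endpoint |
|---|---|---|---|
| 10% | 0.012-0.013 | 0.022-0.023 | 0.033-0.035 |
| 30% | 0.019-0.020 | 0.022 | 0.040-0.041 |
| 50% | 0.021-0.022 | 0.022-0.023 | 0.041-0.044 |

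Allowing for variation between runs, the range is about 0.032 to 0.044. It lies below 0.05 because the discrete s-BA test is conservative, most of all at a low responder rate.

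**3. Error with a serial gate (second endpoint tested only if both doses succeed on the regional primary).** There are two cases.
- At least one dose is truly ineffective on the primary. Opening the gate then requires rejecting that true null, which is already an error on the primary. Any error therefore implies a primary error, which the closed test holds at 0.025.
- Both doses are effective on the primary. Errors can then occur only on the second endpoint, whose own closed test holds them at 0.025.

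The simulated null error is 0.012-0.022 with s-BA first and 0.022-0.023 with pruritus first, the same as for the primary alone.

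**4. Why the gate must require both doses.** Let one dose work on s-BA and the other three hypotheses be null (assumed rates 95% and 30%). The simulated error is 4.6-4.8% with no gate, 3.6-3.8% with a dose-by-dose gate, and 2.7% with the both-doses gate. The excess of the last over 2.5% comes from the large-sample CMH test, not from the gate.

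**5. Chance of a controlled second claim for a given dose.** Under independence it is (both-dose power on the primary) × (per-dose power on the second endpoint). With the stated figures:
- EU/RoW, pruritus second: 0.91 × 0.89 = 0.81.
- US, s-BA second: 0.83 × 0.94 = 0.78.

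The joint simulation gives 82-83% for pruritus behind s-BA, and 79-81% for s-BA behind pruritus (79-80% in one set of runs, 80-81% in another). Ungated per-dose power is about 90% and 95%, so the reduction is about 7 to 15 points.

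**6. How often the gate stays shut at the stated powers.** 100 - 91 = 9% of trials with s-BA first; 100 - 83 = 17% with pruritus first.

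**The case against.** The best defence is that the design is coherent as it stands. The objectives belong to the trial as a whole, and each has a confirmatory analysis somewhere: s-BA response for EU/RoW, pruritus for the US. Nothing in the protocol promises that both will be confirmatory for every regulator. Secondary results are described as supportive, and whether to seek a controlled second claim is for the sponsor and regulators to choose. All of this stands.

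It also disposes of two stronger readings. A reader might infer that the plan exceeds its own 0.025. It does not: that level is stated for the two dose comparisons within each primary endpoint, not across endpoints, and within that scope it holds. A reader might also infer that one primary objective has no controlled test at all. That is not so either; the gap exists only within a region.

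One textual doubt remains. The sentence just before the no-adjustment rule opens with *Other*, which could be meant to set the two swapped endpoints apart. But the no-adjustment sentence carries no such limit, and no procedure is given for either endpoint in its secondary role. The blanket reading is the natural one; if it was not intended, the text still needs correcting.

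Nor is the gate free for the second endpoint: a nominal test at about 90% or 95% power becomes a controlled one at about 82-83% or 80%.

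**Conclusion.** The point holds as a missed opportunity, not as a breach of error control. In each region one of two powered primary objectives is confined by a stated rule to a nominal result, although one linking sentence would give it a controlled test. The either-endpoint error of about 0.032-0.044 arises only if a significant second endpoint is treated as a claim, which the protocol does not say it will be. That range rests on the assumed null responder rate and correlation; the bound of 0.05 does not. The argument that the gate controls error needs neither assumption, but it presumes that each endpoint's test holds its nominal level, which the large-sample CMH test may slightly miss. The power figures rest on the protocol's assumed effects and on simplified tests without strata or covariates. The change is worth making, but the trial's primary inference does not depend on it.

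**What to change.** In section 11.2.2.1 and the synopsis, state that in each region, if both doses are significant on that region's primary endpoint, the other region's primary endpoint is tested next with the same pooled-then-individual closed procedure at one-sided 0.025. State that all other secondary and exploratory endpoints remain unadjusted and supportive. Make the change before unblinding and carry it into the SAP. Specify the both-doses condition explicitly, since a dose-by-dose gate does not hold the level.

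The cost is wording only: no added patients, visits or assessments, and no change to the level or power of the regional primary. Where either dose misses on the primary, no controlled second claim is possible, even if the other dose clearly works; the second endpoint is then reported nominally, as it would be now.

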#### **11.2.2.2 Missing Data**

In the primary analysis of the pruritus endpoint, all intermittently missing assessments will be classified as negative pruritus assessments. Similarly, all planned assessments after the intercurrent events (premature treatment discontinuation, death or initiation of rescue treatments such as biliary diversion surgery or liver transplantation) will be counted as negative pruritus assessments. However, as described above, all 336 assessments planned over the 24-week treatment period will be included in the denominator of the endpoint definition.

In the primary analysis of fasting bile acid responder endpoint, dropouts and patients with a missing average at the end of the treatment will be treated as non-responders. Patients in need of surgical rescue, i.e. biliary diversion and listing for liver transplant will be classified as non-responders. Continued collection of efficacy data for patients who discontinue treatment will be made as far as possible.

#### **11.2.2.3 Demographic and Baseline Characteristics**

Descriptive summaries of demographics and other baseline characteristics (including medical and surgical history) will be presented by treatment group and overall using the FAS.

Prior and concomitant medication use during the study will be summarized by treatment group and overall using the safety analysis set.

#### **11.2.2.4 Subject Disposition**

The following will be summarized (by treatment group and overall where applicable):

- Patients enrolled (who signed the informed consent)
- Patients randomized
- Patients treated
- Patients completing the study
- Patients withdrawing early (including withdrawal reason)

Additionally, patients enrolled, included in the safety, in the FAS, and in the PP analysis set will be summarized by region.

#### **11.2.2.5 Evaluation of Primary Efficacy Variables**

For EU and RoW, the primary responder endpoint based on change in fasting bile acids will be analyzed in terms of the proportion of patients achieving the event of interest. Patients in need of surgical rescue, i.e. biliary diversion and listing for liver transplant, will be classified as non-responders. Dropouts will be treated as non-responders.

CMH stratified by PFIC class and age class will be performed to compare the proportion in fasting bile acid responders at the end of treatment (Week 22 and 24) in the two A4250 dose groups to the placebo group. To ascertain that all data are used in the CMH analysis, neighboring strata will be pooled if all subjects in a stratum have the same response. The proportion together with corresponding 95% CI, odds ratio and corresponding 95% Clopper-Pearson exact CI and p-value for the CMH test will be presented

Logistic regression will be performed as a supportive analysis to compare the proportion in fasting bile acid responders at the end of treatment (Week 22 and 24) in the two A4250 dose groups to the placebo group. The model will include treatment arm, baseline value, and randomization stratification factors, i.e. PFIC class and age class. Baseline value will be calculated as the average of serum bile acid values at randomization and the previous visit (Clinic Visit 2).

In the US, for the primary efficacy variable of the proportion of positive pruritus assessments at the subject level over the 24-week treatment period, ANCOVA will be used to analyze the pruritus endpoint. The model will include treatment arm, AM baseline pruritus score, PM baseline pruritus score, and randomization stratification factors, i.e. PFIC class and age class. LS mean(SE) by treatment arm and LS mean difference (SE), 95% confidence intervals, and p-values (where applicable) between treatments (120 µg/kg/day and 40 µg/kg/day, respectively) vs. placebo will be provided. If there are concerns on model assumptions, i.e. normality and homogeneity of variances, a non-parametric ANCOVA based on the rank scores can be used. LS mean/SE on the outcome by treatment arm and LS mean difference/SE between active dose and placebo will be provided.

Sensitivity analysis will be conducted to assess the impact of intermittently missing data as well as intercurrent events and will be specified in the SAP. Subgroup analyses will also be performed for each of the 3 age groups (6 months to 5 years, 6 to 12 years, and 13 to ≤18 years) and for patients who were not included in the previous Study A4250-003.

#### **11.2.2.6 Evaluation of Secondary and Exploratory Efficacy Variables**

The change in the secondary endpoints such as serum bile acids, total bilirubin, ALT, growth, Albireo PRO and ObsRO sleep parameters, and patient-reported itch severity will be

summarized by visit using descriptive statistics. Change in growth (weight for age and BMI for age) will also be displayed using graphical presentations.

Proportion of responders at Weeks 12 and 24 based on the PRO/ObsRO instruments estimated from both distribution and anchor-based approaches will be analyzed using the same model as specified for the primary analysis for EU and RoW.

Proportion of individual assessments meeting the definition of a positive pruritus assessment at the subject level from Weeks 0-4, Weeks 0-8, Weeks 0-12, Weeks 0-18, Weeks 0-24, respectively, or the proportion of positive pruritus assessments at each 4-week interval over the 24-week treatment period for AM or PM, respectively will be analyzed using the same model as specified for the primary analysis for US.

Undergoing biliary diversion surgery and/or liver transplant, all-cause mortality, and liver decompensation events will mainly be analyzed by using descriptive statistics. Kaplan-Meier curves will be used when appropriate for time to event data.

Comparisons of the change from baseline at Week 24 in PedsQL between the treatment groups will be conducted using ANCOVA. The model will include terms for baseline, PFIC class, age class, and treatment.

Other exploratory variables (Global Symptom Relief, biochemical markers and measures of bile acid synthesis, additional Albireo PRO and ObsRO sleep parameters, PELD/MELD score, APRI score, and Fib-4 score) will be analyzed descriptively for categorical and continuous data, as applicable. For continuous data, the change from baseline will be analyzed in addition to the actual visit values. For categorical data, shift tables or frequency and percentages of patients will be presented as appropriate. Additional details on secondary and exploratory efficacy variables and subgroup analyses by age class (6 months to 5 years, 6 to 12 years, and 13 to  $\leq 18$  years) will be specified in the SAP.

